#### **4.8.3. Cost-effectiveness analysis outcomes**

- Incremental cost per SSI prevented
- Incremental cost per QALY

**Figure 3:** Summary of Study Flow and Procedures

## **5. Data Management**

### **5.1. Data Collection**

We will collect detailed antepartum, intrapartum, and postpartum information from study participants into a comprehensive database.

- Trained research staff in obstetric and perinatal outcomes abstraction at each center will be responsible for all research data abstraction from patient records
- Research staff will undergo centralized specific training to ascertain study outcomes
- Standardized information will be abstracted from all charts regardless of study group
- Relevant data will be collected initially to assess eligibility. Complete baseline, outcome, wound culture, and cost data will be collected via direct interview and chart review
- Several data collection forms will be used during these processes, including forms for maternal baseline data, preoperative and intraoperative care, maternal outcomes, postpartum clinic/hospital outcomes, and Quality of Life Questionnaire (EQ-5D-3L)
- Data on these forms devoid of personal identifiers will be securely sent to the data management center through web-based entry

### **5.2. Specimen collection and storage for future studies**

- Subjects will be asked to participate in an optional biospecimen collection in which their samples will be stored for batched analysis. These samples may be used for future research studies or shared with other researchers. These samples may include:
  - Skin swabs at the incision site before skin prep
  - Skin swabs at the incision site after skin prep
  - Subcutaneous adipose tissue biopsy prior to fascial incision
  - Subcutaneous adipose tissue biopsy after fascial closure
- All specimens will be processed per the Manual of Operations and stored at -80 degrees Celsius +/-2 degrees until analysis

### **5.3. Data Processing**

The Data Management Center (DMC) at Washington University School of Medicine will be responsible for data management and analysis in accordance with the analysis plan to be finalized by the steering committee and approved by the DSMB. The Data Management Team based at Washington University includes an experienced statistician and a database manager. Each site PI and nurse coordinator will be responsible for liaison with the DMC including transmitting de-identified abstracted information contained in the data collection forms. Data management at each site will include: procedures for data entry, data editing, and compilation; procedures for data transmittal; and procedures for quality control, data verification, confidentiality and security. Data will be collected and managed with REDCap (Research Electronic Data Capture), an established, secure, web-based data capture and management tool developed at Vanderbilt University and supported by the bioinformatics team at WUSM (<http://www.biostat.wustl.edu/redcap/>). The security of the database will be maintained by the use of dedicated password protected encrypted computers with multiple private backups (daily, weekly, and monthly including on- and off-site storage for protection against disaster).

### **5.4. Loss to follow-up and missing data**

We will employ strategies we have used in prior studies to achieve excellent follow-up and minimal missing data. Because patients will require necessary postoperative and postpartum visits, there will be ample opportunity for follow-up. In addition, we will obtain two contact numbers from subjects when available and contact them on approximately postoperative day 30 ( $\pm 2$  days). We will also obtain written authorization to obtain records from their Emergency Room and physician office visits and hospital readmissions. We will employ active data management at each site, including monthly data review for rates and patterns of missing data. Remedial measures including re-abstraction of data and retraining of staff will be used as needed to minimize missing data. If data are still missing, we will address the deficiency analytically. We will first determine if data is missing at

random. We will then employ methods including multiple imputations and sensitivity analyses to test the robustness of our results.

## **6. Data Analysis**

### **6.1. Sample Size and Power**

#### **6.1.1. Primary Aim – Effectiveness**

The total sample size for the trial is estimated based on the primary outcome. We then estimate, on the basis of the sample size for the primary aim, the power we will have to detect clinically significant differences in the secondary aims. All sample size and power estimates are based on two-tailed tests, enabling us to detect an increase or decrease in rates of outcomes with use of prophylactic NPWT.

The baseline rate of SSIs in obese women from our preliminary data is 11.6%. Furthermore, rates of SSIs at the study sites in all women range from 6 to 12% and are expected to be higher in obese women. Assuming a conservative baseline rate of 10%, we estimate that a total of **2850** subjects (1425 NPWT and 1425 standard care) will be sufficient to detect a 30% relative difference in SSIs, with 80% power and 5% significance level and

**Table 4: Sample size estimation**  
(Power=80%, 2-tailed,  $\alpha =0.05$ )

Detectable relative difference	Anticipated SSI rate with NPWT (assuming 10% baseline rate)	Sample size (assuming 5% loss to follow-up)
50%	5.0%	910
40%	6.0%	1514
33%	6.7%	2316
30%	7.0%	2850
25%	7.5%	4215
20%	8.0%	6760

accommodation of 5% loss to follow-up (Table 4). This 30% difference represents the difference between a 10% rate of SSI in the standard care group and a 7% rate in the NPWT group.

#### **6.1.2. Secondary Aim 1 - Safety**

The sample size of 2,850 subjects for the primary aim will be sufficient to detect at least a 25% difference in composite adverse events between the two groups with 85% power and significance

level of 5%. This represents the difference between a 16% rate of composite adverse events with NPWT (based on preliminary data) and 12% with standard dressing.

### **6.1.3. Secondary Aim 2 – Cost Effectiveness**

A recent cost-effectiveness analysis estimated a 400 to 600 patients as the adequate sample size of a future trial investigating cost- effectiveness of prophylactic NPWT at cesarean. Thus, our sample size of 2850 for the primary outcome will provide sufficient power for the cost-effectiveness analysis.

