#### *Cost-Effectiveness Analysis*

The economic analysis will be led by [name], MPP, MPH, PhD, an MFM Specialist and Health Economist with extensive experience in cost-effectiveness analysis. We will adhere closely to the guidelines for economic analysis accompanying clinical trials set forth by the international Task Force on Good Research Practices on RCT Cost-Effectiveness Analysis. The primary perspective of this economic evaluation will be societal, but we will also examine the patient and health care payer perspectives. This analysis will follow the intention-to-treat principle. The time horizon for the analysis will be the 30-day follow-up period of the trial, but we will include costs for treatment of SSIs beyond 30 days. Costs and effects will not be discounted because the time horizon for the analysis is short.

**Costs:** Direct medical costs will be the primary measure, but indirect costs may be considered if feasible. Direct medical costs will include the cost of implementing prophylactic NPWT or standard dressing (e.g., device or dressing cost, treatment of side effects), and medical care for SSI (e.g., hospital costs, emergency room, outpatient services, wound care supplies, and medications). Indirect costs will include cost of traveling for outpatient visits and lost productivity from being absent from work or usual activity. Secondary data sources will be used as much as possible to reduce the burden of data collection for economic analysis. Unit costs for inpatient and outpatient services, outpatient procedures, laboratory tests, and office visits will be estimated by using charges adjusted for cost-to-charge ratios. The unit cost of medications will be derived from average wholesale prices. Unit costs for study patients' time will be based on the average national wage rate.

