**Effectiveness:** The effectiveness measures will be rate of SSI and QALYs. We will calculate QALYs by applying utility weights (1=perfect health, 0=death) to various health states values derived from the EuroQol five dimensions questionnaire (**EQ-5D**). The EQ-5D is a standardized instrument for measuring generic health status. The health status measured with EQ-5D-3L is used for estimating preference weight for that health status, then by combining the weight with time, QALYs can be computed. We will administer the EQ-5D to patients at the 30-day follow-up phone call. Once the data have been collected a scoring function can be used to assign a value (i.e., EQ-5D™ index score) to self-reported health states from a set of U.S.-generated value set (preference weights).

EQ-5D is one of the most commonly used generic health status measurement, and its good validity and reliability have been reported in various health conditions. The EQ-5D-3L questionnaire is made up for two components; health state description and evaluation. In the description part, health status is measured in terms of five dimensions (5D); *mobility, self-care, usual activities, pain/discomfort, and anxiety/depression*. Mobility dimension asks about the person's walking ability. Self-care dimension asks about the ability to wash or dress by oneself, and usual activities dimension measures performance in "work, study, housework, family or leisure activities". In the pain/discomfort

dimension, it asks how much pain or discomfort they have, and in the anxiety/depression dimension, it asks how anxious or depressed they are. The respondents self-rate their level of severity for each dimension using a three-level (3L) scale: *having no problems, having some or moderate problems, being unable to do/having extreme problems*. In the evaluation part, the respondents evaluate their overall health status using the visual analogue scale (EQ-VAS) which ranges from 0 (the worst health you can imagine) to 100 (the best imaginable health state).

**Cost-effectiveness:** The measures of cost-effectiveness of prophylactic NPWT will be incremental cost per case of SSI prevented and incremental cost per QALY. They will be calculated as follows.

Incremental cost per case of SSI prevented:

$(\text{Mean Cost}_{\text{Prophylactic NPWT}} - \text{Mean Cost}_{\text{standard care}}) \div (\text{Mean SSI Rate}_{\text{Prophylactic NPWT}} - \text{Mean SSI Rate}_{\text{standard care}})$

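### The claim that 2850 women give sufficient power for the cost-effectiveness analysis is not supported for cost per QALY, the only measure with a decision rule

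*Combined protocol and SAP*

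**What the plan says.** Section 6.1.3 of the combined protocol and SAP consists of two steps. A cited cost-effectiveness analysis put the adequate size of a future trial at 400 to 600 patients. From this the plan concludes: "Thus, our sample size of 2850 for the primary outcome will provide sufficient power for the cost-effectiveness analysis".

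Section 6.2.2 (Cost-Effectiveness Analysis) sets out what is to be estimated. On the horizon: "The time horizon for the analysis will be the 30-day follow-up period of the trial", although SSI treatment costs after day 30 are also counted. On utilities: "We will administer the EQ-5D to patients at the 30-day follow-up phone call". Neither that section nor Section 4.6 names any other administration of the instrument. There are two measures, incremental cost per SSI prevented and incremental cost per QALY. Only the second has a decision rule: the device is to be called cost-effective if the ratio is below $100,000. Confidence intervals, sensitivity analyses and Monte Carlo simulation are planned.

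For the primary outcome, by contrast, Section 6.1.1 gives its inputs in full: two-sided testing at 5%, 80% power, 1425 per arm, "accommodation of 5% loss to follow-up", and "a 10% rate of SSI in the standard care group and a 7% rate in the NPWT group".

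**The concern.** A power statement needs an effect, a measure of spread and a criterion. Sections 6.1.1 and 6.1.2 supply rates, power and significance level for the SSI and safety outcomes. Section 6.1.3 supplies nothing comparable for costs or QALYs, and it borrows its number from a source whose assumptions are not stated.

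The design also makes precision on QALYs doubtful. The horizon is 30 days, the plan names one EQ-5D measurement at its end, and the planned SSI difference is 3 percentage points. An infection that has cleared by the call may leave little trace in the score.

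At stake is how a secondary aim will be read. If the QALY difference is close to zero relative to its error, cost per QALY is unstable and its interval can be unbounded, while readers have been told that the analysis is adequately powered.

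**Working it through.** **1. The plan's own figure.** For 10% against 7%, two-sided 5%, 80% power and a pooled-variance test without continuity correction, the requirement is 1356 per arm, or 2712 in total. Allowing for 5% loss, 2712 / 0.95 = 2855, which agrees with 2850 to rounding. So 2850 is right for SSI. No cost-effectiveness power figure is stated, so none can be reproduced.

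**2. Does the cited size transfer?** At 10% against 7%, power for the SSI difference is about 18% with 400 women and 25% with 600 after 5% loss, or 19% and 26% without loss. Table 4 asks for 910 even for a halving of SSI. The 400 to 600 must therefore rest on another effect or another criterion, neither of which is given. The inference in Section 6.1.3 does not follow from this trial's assumptions.

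**3. QALY difference relative to its standard error.** From the documents: SSI difference 0.03; 1425 × 0.95 ≈ 1354 evaluable per arm; horizon 30/365 = 0.0822 year. Not in the documents, so assumed: utility loss per SSI *d*; the fraction *f* of the 30 days over which it counts; the between-patient SD of the EQ-5D index. Two structural assumptions are also needed: QALYs are patient-level EQ-5D values, and the gain arises through averted SSIs.

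- Expected difference = 0.03 × *d* × *f* × 0.0822
- Standard error = SD × 0.0822 × √(2/1354) = SD × 0.0822 × 0.03843
- Ratio = (0.03 / 0.03843) × (*d*/SD) × *f* = 0.78 × (*d*/SD) × *f*; the horizon cancels

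With *f* = 1, the loss needed is:

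| Ratio | Utility loss needed |
|---|---|
| 1 | 1 / 0.78 = 1.28 SD |
| 1.96 | 1.96 / 0.78 = 2.5 SD |
| 2.80 (80% power) | 2.80 / 0.78 = 3.6 SD |

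For example, take *d* = 0.20 and SD = 0.15:

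- Loss for 14 days: difference 0.00023, standard error 0.00047, ratio 0.49, power 7%.
- Loss for all 30 days: difference 0.00049, ratio 1.04, power 18%. About 20,700 women would be needed for 80%.

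Over an assumed grid of 96 combinations (*d* of 0.05, 0.10, 0.15, 0.20, 0.30, 0.40; SD of 0.10, 0.15, 0.20, 0.25; 7, 14, 21 or 30 days) the ratio runs from 0.04 to 3.12. It is below 1 in 78 and below 1.96 in 92. Power reaches 80% in one: *d* = 0.40 for 30 days with SD 0.10, at 88%.

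**4. What the QALY gain can be worth.** If every SSI removed all utility for the full 30 days, the averted-SSI gain would be 0.03 × 30/365 = 0.0025 QALY per woman, or about $247 at $100,000 per QALY. Section 2.3 puts the study device at about $500. Even in that extreme case, averted costs would have to reach about ($500 − $247) / 0.03 ≈ $8,450 per SSI prevented to break even, ignoring the cost of the standard dressing.

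**5. Net benefit at the threshold.** Assume *d* = 0.20 for 30 days, SD 0.15, and independent costs and QALYs. The QALY standard error is worth about $47. Net benefit = $49 − ($500 − 0.03 × cost per SSI). The cost standard error is 0.03843 × cost SD.

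| Assumed cost per SSI | Net benefit | Power at cost SD $2,000 | $5,000 | $10,000 |
|---|---|---|---|---|
| $3,000 | −$361 | 98% | 45% | 15% |
| $10,000 | −$151 | 39% | 12% | 6% |
| $20,000 | +$149 | 38% | 11% | 6% |

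One of the nine combinations reaches 80%. The result turns on the cost SD, which the plan does not give.

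**6. Cost per SSI prevented.** The denominator has ratio 0.03 / √(0.10 × 0.90/1354 + 0.07 × 0.93/1354) = 2.80, which is 80% power.

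**The case against.** The strongest reply is that the calculation in step 3 models only one reading of the plan.

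- **Health-state model.** Section 6.2.2 speaks of applying weights to health states and of sampling parameters within a model. That also fits an analysis in which the QALY difference is the SSI difference times an estimated utility loss. With losses of 0.05 to 0.30 for all 30 days, SDs of 0.10 to 0.20 and about 230 SSIs (0.085 × 2708), the ratio is then 2.2 to 2.8, against 0.20 to 2.34 at patient level.
- **Effects in women without SSI.** Pain, seroma, hematoma and blistering are secondary outcomes in Section 4.8.2, and EQ-5D has a pain dimension. An assumed mean difference of 0.02 between arms would be 0.02 / (0.20 × 0.03843) = 2.6 to 0.02 / (0.10 × 0.03843) = 5.2 standard errors.
- **QALY noise matters little to net benefit.** It is worth about $47 in the example.

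All three stand. They rule out inferring that 80% power can never be reached, or that the gain can come only from the 3% of women spared an SSI; the first depends on the chosen ranges and the second is an assumption. But none of them supplies what Section 6.1.3 lacks, and the third moves the burden to a cost SD that is not stated.

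It can also be said that the planned intervals and simulations will show any imprecision. They do so only in part. When the QALY difference is not clearly separated from zero, an interval for the ratio can be unbounded. A device that raises cost and lowers QALYs gives a negative ratio, which literally satisfies a rule of less than $100,000.

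**Conclusion.** Sufficient power is not shown for cost per QALY. That conclusion needs no outside figure: Section 6.1.3 gives no effect, SD or criterion, and the cited size gives only about 18% to 26% power at this trial's own SSI rates.

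The size of the shortfall is conditional. With patient-level QALYs and gains through averted SSIs, 80% power needs a loss of about 3.6 SD for all 30 days; a health-state model or effects in other women could be more favourable. On averted-SSI gains, the bound of about $247 against about $500 means that the verdict depends mainly on costs, whose expected difference and SD are absent.

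A reader might go further and infer that the whole economic analysis is underpowered, or that the plan contains an arithmetic error. The documents support neither. The denominator of cost per SSI prevented has 80% power, 2850 reproduces for the primary outcome, and Section 6.1.3 contains no calculation that could be wrong. The fault is an unsupported statement about a secondary aim. It should be corrected, but the primary test and the sample size are untouched.

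**What to change.** In Section 6.1.3, delete the power claim for the per-QALY analysis, or limit it to the SSI denominator. Describe the per-QALY analysis as estimation, and give its expected precision under stated SDs for cost and QALYs.

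In Section 6.2.2, say whether QALYs are patient-level values or come from a health-state model. Base the $100,000 decision on incremental net monetary benefit with a 95% confidence interval and an acceptability curve. Unlike the ratio, net benefit stays well defined when the QALY difference is near zero or negative.

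The cost is a less favourable statement in the plan and a little more analysis. No additional women or visits are needed.

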## **6.2. Data Analysis Plan**

### **6.2.1. Primary Analyses**

Data analyses will adhere closely to the CONSORT guidelines. Analyses will follow the intention-to-treat principle in which subjects will be analyzed in the group to which they were randomized, regardless of whether or not they received the assigned intervention.

Descriptive statistics will characterize the group of individuals recruited and investigate comparability of the two groups at baseline. Formal statistical testing will be limited to selected baseline characteristics considered to be prognostic factors for the primary outcome such as emergent cesarean, type of skin incision, and prolonged rupture of membranes. The categorical prognostic factors will be compared between trial groups by using the Chi-squared or Fisher's exact tests as appropriate. The two-group independent t-test and Mann-Whitney U test will be used to compare normal and non-normally distributed continuous variables, respectively. The primary outcome and other categorical secondary outcomes will be compared between intervention groups by using the Cochran-Mantel-Haenszel test. We will calculate common relative risks and 95% confidence intervals associated with the primary and secondary outcomes.

We will use the Breslow-Day test to assess homogeneity of the effect across subgroups (study sites, BMI category [30 – 39.9,  $\geq 40$ ], and scheduled/non-labor or unscheduled/labor cesareans, skin incision type [low transverse, high transverse, midline vertical], diabetes status). We will also conduct time-to-event analyses by using Kaplan Meier and Cox regression models to examine the pattern of SSIs in the two groups.

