## 1.2. Specific Aims

**Primary Aim:** Determine the effectiveness of prophylactic NPWT in reducing the rate of SSIs after cesarean in obese women. *We hypothesize that obese women will have lower rates of SSIs after cesarean with use of prophylactic NPWT than with standard care.*

**Secondary Aim#1:** Assess the safety of prophylactic NPWT in obese women as measured by frequency of adverse events including skin blisters, allergic skin reactions, and wound bleeding. *We hypothesize that the rate of adverse events will not be significantly higher with use of prophylactic NPWT than with standard care.*

**Secondary Aim#2:** Evaluate the cost-effectiveness of prophylactic NPWT compared with standard wound dressing in obese women as measured by the incremental cost per case of SSI prevented and per quality-adjusted life year (QALY). *We hypothesize that prophylactic NPWT in obese women at cesarean will be cost-effective.*

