#### *Preliminary Study#1*

We conducted a retrospective cohort study at one of the proposed study sites (University of Alabama at Birmingham) where some physicians use the NPWT in select morbidly obese women undergoing cesarean. The charts of all women with a BMI  $\geq 40$  kg/m^2 undergoing cesarean since NPWT became available were reviewed. Of 762 subjects, 15

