#### **3.2. Design and Rationale**

This is a pragmatic multicenter randomized controlled trial. We chose a randomized controlled trial, the 'gold standard' of clinical research design, with the goal of obtaining the highest quality evidence to inform clinical practice. The broad inclusion criteria and evaluation of effects of typical use of prophylactic NPWT make this a pragmatic trial. The multicenter design and inclusion of both academic and community hospitals in two regions of the U.S. with high rates of obesity increase generalizability and direct application of the findings. We will follow the Consolidated Standards of Reporting Trials (CONSORT) guidelines in the conduct and reporting of this trial. Analysis will follow the intention-to-treat principle. By random allocation, patients will receive either prophylactic NPWT or

standard wound care after cesarean delivery. The remainder of perioperative care will be similar for both arms including the administration of standard preoperative antibiotics within 60 minutes prior to skin incision, skin preparation with chlorhexidine alcohol or povidone-iodine solution, and clipping (rather than shaving) of hair as needed prior to incision.

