#### **4.8.2. Secondary Outcomes**

[figure not shown]
- Individual components of the primary outcome (superficial or deep SSI)
- Organ space SSI (endometritis)
- Other individual wound complications: dehiscence  $\geq 2$  cm, hematoma, seroma, erythema

- Composite of any wound complications
- Patient pain and satisfaction scores at discharge and postoperative day 30
- Patient satisfaction with aesthetic appearance (scale of 0 - 10) at postoperative day 30
- Healthcare resource utilization: physician office or ED visits, antibiotics for SSI, hospital readmission for SSIs, home health for SSI, wound clinic for SSI
- Adverse events: skin blistering, allergic reaction, wound bleeding

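### Dressing-related adverse events are compared only by randomized arm; a supportive comparison by dressing actually received should be added, because any switching favours the safety hypothesis

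*Combined protocol and SAP*

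**What the plan says.** Section 3.2 states the rule without a safety exception: "Analysis will follow the intention-to-treat principle". Section 6.2.1 spells it out: "subjects will be analyzed in the group to which they were randomized, regardless of whether or not they received the assigned intervention".

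The dressing reactions come under that rule. Section 4.8.2 lists among the secondary outcomes "Adverse events: skin blistering, allergic reaction, wound bleeding", and section 6.2.1 gives the test: "The primary outcome and other categorical secondary outcomes will be compared between intervention groups by using the Cochran-Mantel-Haenszel test". Neither section 6.2.1 nor section 6.2.2 defines a safety, as-treated or per-protocol set.

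The safety aim in section 1.2 reads: "We hypothesize that the rate of adverse events will not be significantly higher with use of prophylactic NPWT than with standard care". The hypothesis under Secondary Question 1 in section 3.1 is equivalent, and neither gives a margin.

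Section 6.1.2 claims 85% power at the 5% level for composite adverse events: "This represents the difference between a 16% rate of composite adverse events with NPWT" "and 12% with standard dressing". It makes no explicit allowance for women who do not wear the assigned dressing.

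**The concern.** Blisters and allergic skin reactions, and to some extent wound bleeding, are local effects that depend on what is on the wound. A woman assigned NPWT who never receives it contributes roughly the standard-dressing risk to the NPWT arm. A control who is given NPWT contributes device reactions to the standard arm. Both pull the two observed rates together.

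For the infection outcome this dilution works against the trial's claim, so it is conservative. For Secondary Aim 1 it works the other way. The hypothesis is supported when no significant excess is found, so poorer adherence makes NPWT look safer. With no companion analysis, a reader of the results could not tell whether a non-significant difference reflects a benign device or incomplete use of it.

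Some switching is conceivable. Preliminary Study #1 (section 2.1.3) reports that at one proposed study site "some physicians use the NPWT in select morbidly obese women undergoing cesarean", section 2.3 describes growing use after cesarean, and allocation is made before the operation (section 4.4).

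**Working it through.** **Inputs from the documents.** Composite adverse event rates are 16% with NPWT and 12% with standard dressing, at the 5% level with stated power of 85% (section 6.1.2). Tests are two-tailed, with 1,425 women per arm and 5% loss to follow-up (section 6.1.1). After loss, 1,425 × 0.95 = 1,353.75, or about 1,354 per arm.

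**Assumed inputs.** Let a be the share of the NPWT arm that does not receive NPWT, and b the share of controls that does. The documents give neither, so they are varied. Risk is taken to follow the dressing worn and to be unrelated to who switches.

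**Step 1: reproduce the plan's power.** For the two-sided normal approximation, power = Φ[(d − 1.96 × SE0) / SE1], where d = p1 − p2, pbar = (p1 + p2)/2, SE0 = √(2 × pbar × (1 − pbar)/n) and SE1 = √((p1(1 − p1) + p2(1 − p2))/n).

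- At n = 1,425: SE0 = √(2 × 0.14 × 0.86/1,425) = 0.01300 and SE1 = √((0.1344 + 0.1056)/1,425) = 0.01298. Then (0.0400 − 0.02548)/0.01298 = 1.119, so power is 0.868.
- At n = 1,354: (0.0400 − 0.02614)/0.01331 = 1.041, so power is 0.851.

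The stated 85% reproduces if the full 4-point contrast is seen between the arms.

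**Step 2: dilute the contrast.** The arm rates become p1 = 0.16(1 − a) + 0.12a and p2 = 0.12(1 − b) + 0.16b, so d = 0.04 × (1 − a − b).

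For a = b = 2%: p1 = 0.1592, p2 = 0.1208 and d = 0.0384. At n = 1,425, (0.0384 − 0.02548)/0.01298 = 0.996, so power is 0.840. At n = 1,354, (0.0384 − 0.02614)/0.01332 = 0.921, so power is 0.821.

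| a (NPWT not received) | b (controls given NPWT) | Difference, points | Power at 1,354 to 1,425 per arm |
|---|---|---|---|
| 0% | 0% | 4.00 | 0.851-0.868 |
| 0% | 2% | 3.92 | 0.836-0.854 |
| 2% | 2% | 3.84 | 0.821-0.840 |
| 5% | 2% | 3.72 | 0.798-0.818 |
| 10% | 3% | 3.48 | 0.746-0.767 |
| 15% | 5% | 3.20 | 0.675-0.697 |

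**Step 3: place the assumptions against the text.** The only site-level figure for NPWT use is in Preliminary Study #1: 15 of 762 women, or 15/762 = 2.0%. It comes from one site and BMI of 40 or more, in routine care outside this trial. It is a rough guide to b, not a crossover rate. No passage gives any figure for a. The last two rows therefore show sensitivity and are not expectations.

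**The case against.** A reader might infer that crossover will be substantial and that the safety comparison will be badly underpowered, at about 0.70 to 0.77. The documents do not support that. Those figures need 10-15% non-receipt, for which there is no source, and control receipt of 3-5%, above the one observed figure of 2.0%. Several features favour receipt: women with contraindications are excluded (section 3.3.2), randomization waits until cesarean is decided (section 4.4), providers must be certified (section 4.2), and the larger dressing takes incisions up to 35 cm (section 4.1). Section 3.2 and Table 2 also set out what the standard arm receives.

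A reader might likewise infer that section 6.1.2 assumes perfect adherence. It does not say so. If its 16% comes from a randomized arm, some non-use may already be built in.

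Nor is intention-to-treat an error here. The trial is pragmatic, and the effect of assignment is a legitimate safety question. A comparison by dressing received is open to confounding: in Preliminary Study #1, NPWT users had a BMI of 68.8 versus 50.0 and more comorbidities. It should not be able to overrule the randomized result.

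All of this limits the size and the form of the remedy. It does not remove the gap. The relatedness rating in section 7.2 is a judgement on each event, and the deviation recording there captures departures one at a time. Neither yields adverse event rates by dressing worn. Section 5.3 refers to an analysis plan still to be finalized, which could add such a comparison, but the present text does not.

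Resting a safety conclusion on non-significance without a margin is a weakness even with full adherence, and a table by dressing received does not cure it.

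**Conclusion.** The point holds as a modest gap. The only planned comparison of dressing-related adverse events is by randomized arm, and any switching biases it toward the hypothesis it is meant to test. The direction follows from the design if a real device excess exists and follows the dressing worn.

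The size cannot be determined from the documents. At 2% switching in each arm the cost is about 3 percentage points of power, and the chance of missing a true 4-point excess rises from about 13-15% to about 16-18%. At 5% and 2% the cost is about 5 points. This warrants a cheap improvement to the plan. It does not show that the safety aim is invalid or that intention-to-treat should be abandoned.

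**What to change.** Keep the intention-to-treat comparison as the main safety analysis. Then:

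- Record on the intraoperative and postoperative forms which dressing was actually applied, any later switch, and the reason.
- Add to section 6.2 a prespecified supplementary comparison by dressing actually received (any NPWT versus none) for skin blistering, allergic reaction, wound bleeding and their composite. Adjust it for site, BMI stratum and scheduled or unscheduled cesarean.
- Report it beside the intention-to-treat result, both with 95% confidence intervals, and give the number who switched in each arm.
- Label it supportive, and do not make Secondary Aim 1 depend on the two analyses agreeing.

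The cost is a few lines in section 6.2, one or two form fields and one table; the sample size is unchanged. The downside is that the added comparison is not protected by randomization, and adjusting for three stratification factors will not remove all confounding.
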